11 ECHOCARDIOGRAPHY PROCEDURES

Hemodynamic function will be evaluated by calculating the number of observations, mean, standard deviation, minimum and maximum values for each of the following variables:

- Mean pressure gradients across the mitral valve
- Peak pressure gradients across the mitral valve
- Cardiac output
- Cardiac index
- Valvular regurgitation

Transthoracic echocardiogram (TTE) examinations are required for each subject at baseline, post-procedure, 30 days, 6 months, 12 months, and annually thereafter for as long as the valve remains implanted.

The study specifies TTE rather than transesophageal echocardiography (TEE) to minimize subject risk. Echocardiographic data collected from TEE warranted for any other medical purpose is allowed.

For Adjunctive EU/CU Subjects, echocardiograms should be collected from subject's medical records, when available, for visits conducted prior to enrollment. Additionally, echocardiograms should be collected even if any echocardiographic assessments occurred outside of a specified visit window as they may be used as supporting source documentation on the subject.

CDs of the echocardiography exams from each required visit will be forwarded to the echocardiography core laboratory (core lab) for interpretation. The primary responsibility of the core lab is to provide consistent interpretation of TTE data across all study sites by completing the TTE Case Report Form (CRF).

The sponsor will use only the measurements from the core lab for analysis. If the core lab determines the echocardiogram is unreadable, the subject may be asked to return for another echocardiogram.

12 BLOOD COLLECTION

Plasma free hemoglobin will be collected and analyzed for hemolysis at baseline, post-procedure, 30 days, six months, 12 months, and annually thereafter for five years as long as the valve remains implanted. Spot urine urobilinogen is an acceptable alternative if a non-hemolyzed blood sample cannot be obtained.

13 DATA COLLECTION PROCEDURES

13.1 Data Entry and CRF Submission

All required data will be recorded on standardized specific Case Report Forms (CRFs).

14 INVESTIGATIONAL DEVICE HANDLING

The sponsor will control the availability of the study valve by shipping valves only to qualified study Investigators who have IRB and sponsor approval. The sponsor will keep records that indicate the destination and date of shipment. Study valves are not transferable between Investigators unless prior written approval is obtained from the sponsor.

14.1 Accountability

Upon receipt of the 15mm MHV, Investigators will maintain the following accurate, complete, and current records relating to device accountability (21 CFR 812.140 (2)):

Records of receipt, use or disposition of study valves including:

- Type and quantity
- Date of receipt
- Location
- Expiration date
- Serial number
- Names of all persons who received, used or disposed of each unit, and
- Why and how many units of the study valve have been used, returned to the Sponsor, repaired, or otherwise disposed of.

All study valves must be accounted for on the Device Disposition Report even if they are not used.

14.2 Storage

The sponsor requires that all study valves be stored according to the labeling, in a secure area to prevent unauthorized access or use. The study site will prevent use of the investigational product for non-investigational procedures.

14.3 Returns

Valves which are expiring, not successfully implanted or are explanted should be returned to the sponsor. All unused 15mm MHV product must be returned to the sponsor at the completion of the study.

Prior to returning study valves, contact the sponsor clinical study team to obtain a return number. Communicate the serial numbers for all valves being returned. After the return number is received, update the applicable Device Disposition Report(s) with the new disposition of the valve, reason for return, and return number. Send a copy of the updated report to the clinical study team by email. Keep the original for your records.

Ensure all opened product is clearly identified. If possible, return the valve in its original packaging and include all components (e.g. valve holder). Include a copy of the Device Disposition Report(s) with the items being returned. Write the return number on the outside of the package and ship to the address provided with the return number.

Safety will be evaluated through the analysis of adverse events related to the 15mm MHV. All valve-related adverse events will be collected and adjudicated by the Data Safety Monitoring Board (DSMB) in accordance with Akins *et al.*²⁵

15.1 Adverse Event Definitions

Adverse Event:

An adverse event (AE) is any undesirable clinical occurrence that is a negative change from baseline.

Unanticipated Adverse Device Effect (UADE):

Any serious adverse effect on health or safety or any life-threatening problem or death caused by, or associated with a device, if that effect, problem, or death was not previously identified in nature, severity, or degree of incidence in the Investigational Plan including a supplementary plan or application); or any other unanticipated serious problem associated with the device that relates to the rights, safety, or welfare of subjects (21 CFR 812.3(s)).

Serious Adverse Event:

Serious adverse events will be defined as those adverse events resulting in the following; death, life-threatening adverse event, inpatient hospitalization or prolongation of existing hospital stay, persistent or significant disability/incapacity or medically significant event.

Non-serious Adverse Event:

Non-serious adverse events will be defined as those events requiring health care professional directed medical intervention but that are not life threatening, and are not likely to have long-term (> 6 months) sequelae, and do not require long term (> 6 months) therapy.

Anticipated Adverse Events:

Complications associated with replacement mechanical heart valves include, but are not limited to:

- hemolysis;
- infections;
- thrombus;
- thromboembolism;
- valve dehiscence;
- unacceptable hemodynamic performance;

- hemorrhagic complications secondary to anticoagulant medication;
- prosthetic failure;
- heart failure;
- damage to other cardiac structures including the cardiac conduction system;
- obstruction or distorting of adjacent cardiac structures; or
- death.

Any of these complications may require reoperation or explantation of the study valve.

15.2 Adverse Event Reporting

15.2.1 Timeline for reporting Serious Adverse Events

The investigator should report all SAEs to the Sponsor as soon as possible but no later than outlined below.

Clinical Site	Reporting timelines
All Sites	SAEs must be reported to the Sponsor no later than 3 calendar days from the day the site personnel became aware of the event or as per the investigative site's local requirements, if the requirement is more stringent than those outlined.

The date the site staff became aware the event met the criteria of an SAE must be recorded in the source document. The Investigator will further report the SAE to the local IRB according to the institution's IRB reporting requirements.

15.2.2 Reporting Valve-Related Adverse Events

Safety surveillance within this trial (and the safety reporting performed by the investigator) starts:

- as soon as the subject is enrolled for Pivotal IDE subjects enrolled under protocol revision A or B.
- as soon as the subject is enrolled for Adjunctive Prospective Subjects.
- from the time of attempted initial implant (defined as the device physically contacting the subject's cardiac anatomy) for enrolled Adjunctive EU/CU Subjects.

Safety surveillance and safety reporting will continue until the last study visit has been performed, or the subject is deceased, or the subject concludes participation in the trial.

Investigators are responsible for promptly reporting, as soon as they become aware, all serious and non-serious valve-related adverse events as specified in Akins et al.²⁵ to the sponsor by

completing the Adverse Event CRF. Serious adverse events should be reported as specified in Section 15.2.1. Reportable events include:

- Death
- Endocarditis
- Hemorrhage (whether or not due to anticoagulant/antiplatelet medication)
- Nonstructural dysfunction (including perivalvular leak, hemolysis, and hemolytic anemia)
- Reoperation (including valve explant, not due to anatomical growth of the subject)
- Structural valve deterioration
- Thromboembolism (valve-related)
- Valvular thrombosis
- Unanticipated Adverse Device Effects (UADEs)

Refer to Appendix 11 for definitions of all reportable valve-related adverse events. All unresolved adverse events should be followed by the Investigator until resolution. Updates to adverse events should be provided to the sponsor by completing the AE Follow-Up CRF.

The sponsor may request that additional information such as operative notes, clinic notes, discharge summaries, histopathology reports, or a physician's summary of the event be provided to the sponsor as supporting documentation for all reported events.

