5 ENDPOINTS

5.1 Primary Safety Endpoint

The primary safety endpoint for this study is the actuarial (Kaplan-Meier) rate of total valve-related adverse events experienced through 365 days post implant or until the valve is removed/replaced due to anatomical growth of the subject, whichever occurs first. Valve-related adverse events to be evaluated are:

- Death
- Endocarditis
- Hemorrhage (whether or not due to anticoagulant/antiplatelet medication) [all and serious]
- Nonstructural dysfunction (including perivalvular leak [all and serious], hemolysis, and hemolytic anemia)
- Reoperation (including valve explant, not due to anatomical growth of the subject) [all and valve-related]
- Structural valve deterioration
- Thromboembolism
- Valvular thrombosis

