15.3 Data Safety Monitoring Board (DSMB)

An independent DSMB will be formed to regularly review study progress with regard to safety. At a minimum, the DSMB will meet semi-annually. Members of the DSMB will have no affiliation with the HALO Clinical Study.

A DSMB Manual of Operations will be developed and agreed upon by the sponsor and DSMB members prior to initiation of the trial. The manual will describe the specific functions of the DSMB. The primary responsibilities of the DSMB are to:

- Establish adverse event definitions (and refine definitions as necessary during the conduct of the clinical study)
- The DSMB will act as a Clinical Events Committee (CEC) to adjudicate whether or not adverse events are valve-related and determine the severity of the events
- Review and validate the subject sample (i.e., review inclusion/exclusion deviations and other protocol deviations)
- Provide oversight for issues affecting general subject welfare
- Establish study termination guideline criteria
- Recommend premature study termination

At any time during the course of the study, the DSMB may offer opinions or make formal recommendations concerning aspects of the study that impact subject safety (e.g., safety-related protocol changes or input regarding adverse event rates associated with the investigational study). Additionally, the DSMB may act as an advisory panel for questions regarding informed consent, subject enrollment, protocol implementation, study endpoints, data discrepancies, and other issues that may present during the course of the study.

The DSMB will review all adverse events reported by the site and determine the following: adverse event type, relatedness to the procedure or device (if known), and whether the event is anticipated or unanticipated. Following each DSMB meeting a report will be sent to Investigators indicating the final adjudication of all adverse events reviewed during the meeting.

In all reports to the FDA adverse events will be pulled from the DSMB adjudication unless the adverse event has not been adjudicated, as noted in the report.

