Examples of nonstructural dysfunction include: entrapment by pannus, tissue, or suture; paravalvular leak; inappropriate sizing or positioning; residual leak or obstruction after valve implantation or repair; and clinically significant intravascular hemolytic anemia. More than mild recurrent or residual mitral regurgitation after surgical or percutaneous interventional valve procedures (coronary sinus interventions, direct reparative methods, or other methods aimed at achieving ventricular remodeling) is nonstructural dysfunction, unless there is disruption of the valve components themselves, which would then be structural deterioration.

Sudden or progressive dysfunction or deterioration of the study valve may be structural, nonstructural, or both as determined by reoperation, autopsy, or clinical investigation.

Reoperation

Reoperation is any operation that repairs, alters or replaces the study valve. The reasons for reoperation are to be reported and may include reasons other than valve-related morbidity, such as recall, excessive noise, or incidental or prophylactic removal.

Thrombolytic or catheter-aided therapy of valve-related morbidity is not considered reoperation; however, the morbid event that prompted the intervention should be reported.

Structural Valve Deterioration

Dysfunction or deterioration involving the study valve (exclusive of infection or thrombosis), as determined by reoperation, autopsy, or clinical investigation will be reported. Structural valve deterioration refers to changes intrinsic to the valve, such as wear, fracture, poppet escape, calcification, leaflet tear, stent creep, and suture line disruption of components (e.g., leaflets) of the study valve.

Thromboembolism

Any thromboembolic event that occurs in the absence of infection after the immediate perioperative period (when anesthesia-induced unconsciousness is completely reversed) will be reported as valve-related. Thromboembolic events occurring during the procedure will be reviewed and adjudicated by the DSMB to determine if the event is valve or procedure related. Subsets of thromboembolic events are:

Neurologic:

A neurologic thromboembolism is one that results in a central, new neurological deficit, whether temporary or permanent and whether focal or global, that occurs after the subject emerges from anesthesia. Types of neurologic events are:

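### An explant labelled as growth can drop out of the primary safety rate with no required independent check of its cause, and 15.2.2 and Appendix 11 disagree on whether it is reportable

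*Combined protocol and SAP*

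**What the plan says.** **Section 5.1** defines the primary safety endpoint as a Kaplan-Meier rate of valve-related events through 365 days "or until the valve is removed/replaced due to anatomical growth of the subject, whichever occurs first". Its reoperation component reads "Reoperation (including valve explant, not due to anatomical growth of the subject) [all and valve-related"]. An explant due to growth is therefore not an event, and it ends the subject's follow-up for this endpoint.

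**Section 15.2.2** uses the same exclusion in its list of reportable events: "Reoperation (including valve explant, not due to anatomical growth of the subject"). It then directs the site elsewhere for the meaning of the terms: "Refer to Appendix 11 for definitions of all reportable valve-related adverse events".

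**Appendix 11, Reoperation**, has no growth exclusion: "Reoperation is any operation that repairs, alters or replaces the study valve". It adds: "The reasons for reoperation are to be reported and may include reasons other than valve-related morbidity".

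**Section 15.3** sets the scope of adjudication: "The DSMB will review all adverse events reported by the site". For each event the DSMB determines "adverse event type, relatedness to the procedure or device (if known), and whether the event is anticipated or unanticipated". The same section also has it judge valve-relatedness and severity, and establish and refine event definitions. Confirming that an explant was due to growth is not among the listed tasks.

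**The concern.** Whether an explant counts in the primary safety rate depends on the cause assigned to it. Growth takes it out; most other causes leave it in. The documents do not define anatomical growth, and neighbouring causes are close to it. Section 7.2 lists mitral stenosis, unacceptable hemodynamics and eventual outgrowth together as reasons for a second replacement. Appendix 11 counts inappropriate sizing as nonstructural dysfunction, which is a component of 5.1. A valve explanted for a high gradient in a growing child could plausibly be described in more than one of these ways.

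If the site calls it growth and follows 15.2.2, the explant need not be entered as an adverse event, and 15.3 then does not bring it to the DSMB. A wrong attribution to growth can only lower the rate or leave it unchanged, so the error favours the device. The study is a single-arm investigation meant to support a PMA supplement (3, 4.1), and no concurrent comparator shares the error. The documents state no performance goal, so what is at stake is how far the rate can be trusted, not a stated pass or fail decision.

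**Working it through.** **Step 1: the two reporting rules side by side.** Take an explant that the site attributes to growth.

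- By the list in 15.2.2, it is excluded from reportable reoperations.
- By Appendix 11, it replaces or removes the study valve, so it is a reoperation and its reason is reportable.

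A site can follow either text and comply with part of the plan.

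**Step 2: the path to the primary endpoint.** Under the first reading no reoperation is reported, the DSMB has no reported event to review, and 5.1 stops the subject's follow-up without an event. Under the second reading the DSMB sees it, but the documents give no criterion for separating growth from the other causes.

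**Step 3: other routes, and whether any requires confirmation of the cause.**

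| Route | What it gives | Confirms growth? |
|---|---|---|
| 15.1 and 15.2.1, serious adverse events | Unacceptable hemodynamic performance is an anticipated event; with hospitalization it is serious and must be reported | Not required |
| Appendix 11, nonstructural dysfunction | Stenosis from an abnormality outside the valve itself is reportable | Not required |
| 9.2 Table 1, explant visit | Echo, examination and event collection before explant | Not required |
| 14.3, valve return | Device Disposition Report carries a reason for return | Not required |
| 5.2 with 11 | Gradients and regurgitation at a growth explant within 12 months are primary effectiveness data, and only core-lab values are analysed | Independent gradient, but no ruling on cause |

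The case that remains is an explant labelled as growth in a subject with no other component event reported.

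**Step 4: size, for illustration.** The documents give no sample size, first-year count of growth explants or event rate to reproduce. Assumptions: N subjects; one disputed explant at day 180; no earlier component event in that subject; no other censoring; k other subjects with an event. The values of k are whole numbers near 5 to 30% of N. That range is the mortality range in 7.2, used only as a stand-in for the composite.

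- Other events after the explant: the rate is (k+1)/N if the explant counts and k/(N−1) if it is censored. The shift is (k+1)/N − k/(N−1).
- Other events before the explant: (k+1)/N against k/N. The shift is 1/N.

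| N | k | Counted | Censored | Shift, events after (points) | Shift, events before (points) |
|---|---|---|---|---|---|
| 15 | 1 | 2/15 = 13.3% | 1/14 = 7.1% | 6.2 | 6.7 |
| 15 | 4 | 5/15 = 33.3% | 4/14 = 28.6% | 4.8 | 6.7 |
| 20 | 1 | 2/20 = 10.0% | 1/19 = 5.3% | 4.7 | 5.0 |
| 20 | 6 | 7/20 = 35.0% | 6/19 = 31.6% | 3.4 | 5.0 |
| 30 | 2 | 3/30 = 10.0% | 2/29 = 6.9% | 3.1 | 3.3 |
| 30 | 9 | 10/30 = 33.3% | 9/29 = 31.0% | 2.3 | 3.3 |

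The Counted and Censored columns are for events after the explant. One reclassified explant moves the rate by 1/N or somewhat less. The shift is zero if the subject already had a component event.

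**The case against.** The strongest reply is that a high-gradient explant is hard to hide. It should reach the sponsor as a serious adverse event or as nonstructural dysfunction, and the DSMB would then assign its type. If it falls within 12 months, its gradient is also a core-lab value in the primary effectiveness data. To stay out of the safety rate, the site must label the explant as growth and also not report the underlying problem; under-reporting of that kind threatens every component. This much stands, and it narrows the point. What it leaves is that a planned replacement for outgrowth may never be judged an adverse event, and that an independent gradient is not an independent ruling on cause.

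Second, the DSMB has to establish event definitions, and its Manual of Operations is not among the documents. A growth rule may be there. That also stands, but the mismatch between 15.2.2 and Appendix 11 would remain.

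Third, a broad definition can coexist with a narrower list, and the 15.2.2 list is introduced as inclusive rather than exhaustive. That reading is possible. But the exclusion expressly narrows this one item, while Appendix 11 wants the reasons reported.

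Fourth, sampling error is larger than the shift. With N=20 and 4 other events before the explant (assumed), the rate is 20.0% with a 95% interval of 8.0 to 44.9%, against a one-explant shift of 5.0 points. True, but the interval does not cover a classification error that runs in one direction.

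**Conclusion.** The point holds and should be fixed; confidence is medium. Sections 15.2.2 and Appendix 11 must be reconciled, and the documents require no independent confirmation of a cause that decides whether an explant enters the primary safety rate.

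A reader might infer more, and the documents do not support it:

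- That growth explants are hidden from the sponsor, or that the site's label alone always decides. The routes in Step 3 make most explants visible and should bring many non-growth cases to the DSMB.
- That the explant echo escapes the core lab. 5.2 and 11 together imply a core-lab reading at a growth explant within 12 months; only the visit list in 11 is incomplete.
- That the label in 5.1 covering all and valve-related reoperations contradicts its growth exclusion. It can be read as two tallies of the reoperations that remain.
- That misattribution has occurred or that the rate is biased by a known amount. Nothing shows this. Section 7.2 calls outgrowth eventual, so there may be no growth explants in the first 365 days and no effect.

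The 2.3 to 6.7 points per explant rest wholly on the assumed N, event counts and timing in Step 4.

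**What to change.** 1. In 15.2.2, require every reoperation or explant to be reported with its reason, in line with Appendix 11.
2. In 15.3, have the DSMB adjudicate whether each explant was due to growth, using existing records and the core-lab echo. Write the criteria down and apply them uniformly, including to explants that have already occurred.
3. Keep the 5.1 exclusion and the primary Kaplan-Meier analysis, but apply the exclusion to the adjudicated cause.
4. Add a sensitivity analysis that counts all explants through 365 days as events.
5. As a consistency edit only, add the explant visit to the list of required echo visits in section 11.

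Cost: a protocol amendment, which under 17.1.2 may need FDA and IRB/EC approval, and a few more cases at existing DSMB meetings. The explant echo and the return of the valve with a reason are already in the plan. For explants that have already occurred, the criteria cannot be called prespecified, and the report should say so. Records will be limited for EU/CU subjects explanted before consent (8.2.3). The reported rate may be less favourable.
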